1.6. Changes of Study Conduct and Planned Analyses

The study did not proceed into Part 2 per decision by study Sponsor and the DRC upon completion of the analyses in all 3 stages in study Part 1. Data from study Part 1 will be summarized with descriptive statistics without formal comparison or hypothesis testing.

2. GENERAL ANALYSIS DEFINITIONS

2.1. Subject Populations

Intent-to-treat (ITT): all participants randomized in Part 1, grouped according to assigned treatment arm. ITT will be used for all summaries of disposition, demographic, baseline disease characteristics, and efficacy analyses.

Modified Intent-to-treat (MITT): all participants randomized in Part 1 who have received at least 1 dose of both study drugs, grouped according to assigned treatment arm. MITT will be used for selected efficacy analyses.

Safety Analysis Set: participants in the ITT population who have received at least 1 dose of study drug. This analysis set will be used for all safety analyses and analyses of exposure.

Pharmacokinetics Analysis Set: participants who have received at least 1 dose of cusatuzumab in combination with azacitidine and whose PK profiles allow for accurate calculation of at least 1 of the PK parameters.

2.2. Definition of Subgroups

Overall response rate will be summarized for the following subgroups:

- Age (<75, ≥75 years)
- Gender (male, female)
- Type of AML (de novo, secondary)
- Cytogenetic risk (adverse, intermediate, favorable)
- Baseline ECOG performance status (0-1, 2)
- Baseline bone marrow blasts (≤50%, >50%)
- ANC (<1.0, ≥1.0 10⁹/L)
- Platelet (<100, ≥100 10⁹/L)

2.3. Study Day and Relative Day

Study Day 1 is the day of randomization for participants randomized in Part 1. By convention, 1 month equals to 30.4375 days, and 1 year equals to 365.25 days. Duration in days between 2 time points will be calculated as (end date – start date + 1).

2.4. Baseline

Baseline value is defined as the last non-missing value collected on or before study Day 1.

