1.3. Schedule of Activities (SoA)

Table 1: Schedule of Activities Up to 22 Oct 2021

NOTE: As of Amendment 3: After 22 Oct 2021, subjects will no longer follow this SoA. Subjects will be treated and assessed according to Table 1A.

	Screening	Randomization	Treatment		Follow-up
Study Procedure	Within 28 days of randomization	Within 72 hours of first dose	Azacitidine/ cusatuzumab combination therapy (28-day cycle)	EOT ^a	30 days (±3 days) after last dose of study treatment and then every 3 months thereafter (±7 days) ^b
			Cycle 1 – EOT		
Screening/ Administrative					
Informed consent ^c	X				
Demographics/ medical history	X				
Cytogenetic testing/ Mutational analysis	X ^d				
Inclusion/exclusion criteria ^e	X	X			
Study Intervention Administration					
Randomization		X			
Pre-medications ^f			X		
Azacitidine 75 mg/m ² SC or IV ^e			Day 1 to Day 7 of each 28-day cycle		
Cusatuzumab IV infusion at selected dose ^f			Day 3 and Day 17 of each 28-day cycle (+2 days)		
Efficacy Assessments					
Disease evaluation ^g	X ^h		Every other cycle, starting at Cycle 1, (between Day 21 up to and including Day 1 of the next cycle) until CR or progressive disease. Once CR is achieved, disease evaluation can be performed every 4th cycle until relapse. Once CR without MRD is achieved, a repeat bone marrow examination to confirm should be performed at least 4 weeks later. In cases of cycle delays, timing of disease evaluations should be performed per protocol at the end of the specified odd cycle.	X	
Bone marrow aspirate ⁱ	Within 7 days of Cycle 1/ Day 1		At every disease evaluation	X	
Evaluation of extramedullary disease ^j	X		At every disease evaluation as needed	X	
Transfusion status	X		At every disease evaluation	X	

	Screening	Randomization	Treatment		Follow-up
Study Procedure	Within 28 days of randomization	Within 72 hours of first dose	Azacitidine/ cusatuzumab combination therapy (28-day cycle)	EOT ^a	30 days (±3 days) after last dose of study treatment and then every 3 months thereafter (±7 days) ^b
			Cycle 1 – EOT		
Survival status/subsequent therapy/ other malignancies				X	X ^k
Safety Assessments (See Section 8)					
Adverse events and concomitant therapy	X		X	X	X
Physical Examination height and weight	X		Day 1 of each cycle (height is measured at screening only)	X	
Vital signs ^l	X		Days 1, 3, and 17 of each cycle	X	
ECOG assessment	X		Day 1 of each cycle	X	

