12-lead ECG ^l	X		For participants with baseline cardiac disease, perform additional ECG every other cycle (at same time as disease evaluation). For other participants, only if clinically indicated		
Spirometry	X (only for participants with baseline pulmonary disease)		For participants with baseline pulmonary disease, perform spirometry every 4th cycle at same time as disease evaluation. For other participants, only if clinically indicated		
Medical resource utilization ^m	Continuous from the time of signing of the ICF until 30 days after the last dose of study intervention				
Clinical Laboratory tests (See Appendix 2, Section 10.2)					
Hematology, including peripheral blood blast counts	X		During Cycle 1: hematology should be checked weekly. For all other cycles, check on Day 1 and Day 17 of each cycle and with each disease evaluation. ⁿ If clinically indicated, monitoring should be more frequent.	X	
Chemistry	X		During Cycle 1: chemistry should be checked weekly. For all other cycles, check on Day 1 and Day 17 of each cycle and with each disease evaluation. ⁿ If clinically indicated, monitoring should be more frequent.	X	
Pregnancy test for women of childbearing potential	X		X	X ^o	
Hepatitis and HIV ^p	X				
Pharmacodynamics and Biomarkers (whole blood/ PBMC/ serum/ bone marrow sample collection)					
PD/ Biomarker testing (See Table 2)	Within 7 days of Cycle 1/ Day 1		See Table 2 for Sampling Schedule		
Pharmacokinetics (Bone marrow and Peripheral blood)					
PK testing (See Table 3 and Table 5)	Within 7 days of Cycle 1/ Day 1		See Table 3 for Sampling Schedule for first 50 participants (25 per group) and Table 5 for participants randomized after the 50 th		

	Screening	Randomization	Treatment		Follow-up
Study Procedure	Within 28 days of randomization	Within 72 hours of first dose	Azacitidine/ cusatuzumab combination therapy (28-day cycle)	EOT ^a	30 days (±3 days) after last dose of study treatment and then every 3 months thereafter (±7 days) ^b
			Cycle 1 – EOT		
Patient-reported outcomes (PRO) ^q					
Fact-Leu			Day 1 of each cycle	X	Only at first visit ^k
EQ-5D-5L			Day 1 of each cycle	X	Only at first visit ^k

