- g. Evaluation includes bone marrow evaluation (bone marrow aspirate preferred for assessment of blast %), hematology with differential, transfusion assessment, and assessment for extramedullary disease per local standard of care. Results of MRD testing will be provided by the Sponsor when appropriate. For participants who discontinue study treatment without disease progression, disease evaluations should continue with the same frequency as during study treatment until disease progression.
- h. Obtain 2 to 3 peripheral blood blast counts during screening
- i. A bone marrow aspirate should be performed for the disease assessment (for bone marrow blasts) within 7 days of first dose (or Cycle 1 Day 1). Once a bone marrow aspirate is performed, the sample must be sent to central laboratory within 48 hours for biomarker and PK testing. In case of a dry tap, a biopsy may also be utilized for disease assessment. See Table 2 for bone marrow biomarker sampling and Table 3 for bone marrow PK sampling. Any unscheduled bone marrow assessments must be reported.
- j. Evaluation for extramedullary disease required only for participants with suspicion of or known extramedullary AML disease
- k. Assessments may occur via telephone contact.
- l. Vital Signs: heart rate, blood pressure (monitor with same method and position [sitting or supine] throughout study), respiratory rate, and temperature to be performed prior to administration of any study intervention. If blood sampling or vital sign measurement is scheduled for the same timepoint as ECG recording, the procedures should be performed in the following order: ECG(s), vital signs, blood draw. See Section 8.2.2
- m. Information on health care needs during treatment (eg, physiotherapist) to be collected by study staff.
- n. Samples may be obtained within 24 hours of the Day 1 and Day 17 visits.
- o. Pregnancy testing to also be performed for women of childbearing potential 1 month after last dose of study treatment.
- p. Laboratory testing for hepatitis and HIV at screening is to be performed for all participants.
- q. PROs should be performed before dosing and before any study tests or procedures or consultations are conducted when possible.

Table 1A: Schedule of Activities After 22 Oct 2021

	Treatment		Follow-up
Study Procedure	Azacitidine/ cusatuzumab combination therapy (28-day cycle)	EOT ^a	30 days (±3 days) after last dose of study treatment and then every 3 months thereafter (±7 days) ^b
	Cycle 1 – EOT		

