8. STUDY ASSESSMENTS AND PROCEDURES

Overview

The Schedules of Activities summarizes the frequency and timing of efficacy, PK, immunogenicity, PD, biomarker, and safety measurements applicable to this study.

If standard of care tests are performed within the allowable screening period but prior to signing of the ICF the results for these tests may be used for determination of participant eligibility. In this case, after the participant signs the ICF, samples for the local laboratory may not be required, however samples for the central laboratory may still be required as referenced in Schedule of Events.

All PRO assessments should be conducted/completed before any tests, procedures (including bone marrow examination), or other consultations to prevent influencing participant perceptions.

Sample collections for PK and PD assessments should be kept as close to the specified time as possible. Other measurements may be done earlier than specified timepoints if needed. Actual dates and times of assessments will be recorded in the source documentation and the eCRF or lab requisition form.

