- At least one question completed

(Note: Items noted as ‘optional’ in the instrument, specifically item GS7 “I am satisfied with my sex life” will not be considered missing for purposes of tabulating PRO completion.)

PRO Overall Instrument Scores

PRO total scores will include the FACT-Leu Total, FACT-Leu TOI, FACT-G, EQ-5D-5L Utility Score, and EQ-5D-5L VAS. (The EQ-5D-5L VAS is a single item but will be categorized with the overall instrument scores as it represents the concept of overall health status.)

For each overall instrument score, a table of descriptive statistics will be presented including mean, standard deviation, median, minimum and maximum at each time point and change from baseline for each post-baseline assessment, by dose group. Each overall instrument score will also be shown in line graphs of mean score and mean change from baseline by dose groups, with 95% CI.

PRO Domain Scores

PRO domain scores will include the FACT-PWB, FACT-FWB, FACT-EWB, FACT-SWB, and FACT-LeuS.

For each instrument domain score, a table of descriptive statistics will be presented including mean, standard deviation, median, minimum, and maximum at each time point and change from baseline for each post-baseline assessment, by dose group. Each overall instrument score will be shown in line graphs of mean score and mean change from baseline by dose groups, with 95% CI.

PRO Item Analyses

Selected individual items from the FACT-Leu addressing concepts of particular interest in the current study context of use will also be described in terms of their category responses. Specifically:

Item number	Item text
GP1	“I have lack of energy”
GP2	“I have nausea”
GP4	“I have pain”
GP5	“I am bothered by the side effects of treatment”
GP6	“I feel ill”
GF1	“I am able to work (including work at home)”

BRM3	“I am bothered by fevers (episodes of high body temperature)”
P2	“I have certain parts of my body where I experience pain”
An7	“I am able to do my usual activities”

For each item, a bar chart will show the distribution of responses (including missing responses), and a second bar chart will show the distribution of change in response categories from baseline (including missing responses).

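### The SAP closes baseline on the randomization day, so a participant first dosed on a later date has no scheduled FACT-Leu or EQ-5D-5L baseline

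*SAP*

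**What the plan says.** SAP 2.4 gives a single baseline rule with no exception for any parameter: "Baseline value is defined as the last non-missing value collected on or before study Day 1". SAP 2.3 fixes the anchor: "Study Day 1 is the day of randomization for participants randomized in Part 1". The same section gives the day count: "Duration in days between 2 time points will be calculated as (end date – start date + 1").

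Protocol Table 1 (Section 1.3) heads the Randomization column "Within 72 hours of first dose". In the FACT-Leu and EQ-5D-5L rows the treatment-phase entry is "Day 1 of each cycle", followed by end of treatment and the first follow-up visit. The Screening and Randomization cells are empty. Footnote q adds: "PROs should be performed before dosing and before any study tests or procedures or consultations are conducted when possible". The overview in Protocol Section 8 allows some flexibility: "Other measurements may be done earlier than specified timepoints if needed".

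SAP Section 6 plans tables of "change from baseline for each post-baseline assessment, by dose group" for five overall and five domain scores, with graphs of mean change. For nine selected FACT-Leu items it plans a chart of the shift in response category from baseline. Protocol 9.4.3 also plans change from baseline. Neither SAP Section 6 nor Protocol 8.9 or 9.4.3 gives a separate baseline definition for the questionnaires.

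**The concern.** The baseline window is tied to randomization, but the first questionnaire is tied to first dose. When the two fall on different dates, the only scheduled pre-treatment questionnaire lands after the window has closed.

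An affected participant then has no reference value for any FACT-Leu or EQ-5D-5L score. That participant drops out of the change-from-baseline tables and graphs and appears as missing in the item-change charts, even if the form was completed correctly before dosing. Who is lost depends on how sites scheduled randomization and dosing, not on whether the questionnaire was filled in.

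**Working it through.** The plan states no figure to reproduce. The check sets the definitions against the schedule and applies the SAP's own day count.

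**Inputs**
- Baseline window: up to and including study Day 1 (SAP 2.4).
- Study Day 1: randomization date (SAP 2.3).
- Day count: end date − start date + 1 (SAP 2.3).
- Gap from randomization to first dose: 0 to 72 hours (Protocol Table 1). Dosing follows randomization and starts on Cycle 1 Day 1 (Protocol 6.1).
- First scheduled FACT-Leu and EQ-5D-5L: Cycle 1 Day 1 (Protocol Table 1).
- Group size: up to 50 per dose group (Protocol 9.2).

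**Study day of the first scheduled questionnaire**

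| First dose relative to randomization date | Study day of Cycle 1 Day 1 | Qualifies as baseline? |
|---|---|---|
| Same date | 0 + 1 = 1 | Yes |
| 1 date later | 1 + 1 = 2 | No |
| 2 dates later | 2 + 1 = 3 | No |
| 3 dates later | 3 + 1 = 4 | No |

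A long delay is not needed. A participant randomized at 16:00 and dosed at 09:00 the next morning has a gap of 8 + 9 = 17 hours, well inside 72. Cycle 1 Day 1 is nevertheless study Day 2, and the predose form is not baseline.

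**Number affected.** Let q be the share of participants dosed on a later calendar day than randomization. The documents do not give q, so it is an assumption with range 0–100%. The maximum lost per dose group is 50 × q:

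- q = 0%: 0
- q = 10%: 5
- q = 50%: 25
- q = 100%: 50

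The Day 1 to Day 4 range shows what the window allows. It does not show how many participants fall on each day.

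**Other parameters.** Hematology, chemistry, ECOG status, vital signs and weight all have a screening assessment, so they keep a qualifying value. In Protocol Table 2, whole-blood flow cytometry, serum cytokines, serum protein quantification and whole-blood gene expression are first sampled predose on Cycle 1 Day 1 with no screening sample. They would share the gap if SAP 2.4 governs them.

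**With a first-dose cutoff.** The predose Cycle 1 Day 1 form qualifies for any gap from 0 to 72 hours, and Cycle 2 Day 1 becomes the first scheduled post-baseline questionnaire for every participant.

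**The case against.** The strongest reply is that the intent is obvious. Footnote q puts the questionnaire before dosing, Cycle 1 Day 1 is the only scheduled pre-treatment form, and an experienced programmer would use it. That is probably so. But it would mean departing from an explicit SAP rule, and nothing in SAP Section 6 authorizes the departure.

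Sites may also collect questionnaires early. This is permitted, not required, so it can rescue individual participants but does not repair the definition.

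The impact may be nil. Same-day randomization and dosing is allowed, so q = 0 is consistent with the documents. The ceiling of 50q also includes participants with no later questionnaire, who would contribute no change score in any case. Both points stand: the mismatch is certain, the amount of data lost is unknown.

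The outputs carry little weight. Patient-reported outcomes are exploratory (SAP 1.1.2), Part 2 will not be run, and SAP 1.6 limits Part 1 to descriptive summaries. This limits the severity and is reflected in the rating.

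Finally, a first-dose cutoff excludes a form completed after dosing on the randomization day, which SAP 2.4 now accepts. That is a real change, but a value taken after treatment has started is not a sound baseline. The cutoff is workable because Protocol Section 8 requires actual assessment dates and times to be recorded.

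**Conclusion.** The concern holds. Followed as written, SAP 2.3 and 2.4 turn the predose Cycle 1 Day 1 questionnaire into a post-baseline value for every participant first dosed on a later date than randomization, and leave that participant without a baseline unless a form was collected early.

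The loss is between 0 and 50 participants per dose group, depending on q. It is confined to the change-from-baseline output for the two questionnaires. Scores at each time point, item response distributions and the protocol's change from previous time point are unaffected, as are all CR, response-duration, PFS and OS results. Low end of should-fix.

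**What to change.** Add one sentence to SAP 2.4 or SAP Section 6: for FACT-Leu and EQ-5D-5L, baseline is the latest non-missing value obtained before the first dose of study drug, normally the predose form on Cycle 1 Day 1. It would help to say in the same place how a form dated on the first-dose day without a recorded time is treated.

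Keep randomization as study Day 1 and as time zero for all other definitions. If SAP 2.4 is also meant to govern the blood markers first sampled predose on Cycle 1 Day 1, extend the sentence to them.

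The cost is the SAP text and a questionnaire baseline flag in the analysis dataset. No new data are required.

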3. SUBJECT INFORMATION

3.1. Demographics and Baseline Characteristics

All demographic and baseline characteristics will be summarized for the ITT population by treatment group and all participants combined.

3.2. Disposition Information

Participant disposition will be summarized for the ITT population by treatment group and total combined with the number and percentages of the followings: study treatment ongoing, discontinued treatment and reason, completed/discontinued the study and reasons.

3.3. Protocol Deviations

Participants with major protocol deviations will be summarized by each category of deviations.

3.4. Prior and Concomitant Medications

Prior and concomitant medications will be coded to generic terms based on the World Health Organization (WHO) dictionary and will be summarized by Anatomical Therapeutic Chemical (ATC) class and drug generic term. Prior anticancer therapies include radiotherapy, surgery, chemotherapy, and systemic therapy.

Premedication for cusatuzumab will be summarized separately.

3.5. Extent of Exposure

The following will be summarized by treatment group, and within each treatment group, by azacitidine and cusatuzumab: total dose prescribed, total dose administered, dose intensity (mg/m²/cycle azacitidine and mg/kg/cycle for cusatuzumab), and relative dose intensity (actual dose intensity divided by prescribed dose intensity).

Total treatment duration in months, total number of cycles, and cycle delay will be summarized by treatment group.

Number and percent of participants who switched the cusatuzumab dose level will also be provided.

4. EFFICACY

4.1. Primary Efficacy Endpoint, CR Rate

Number and percent of participants achieving CR will be provided by treatment arm and the 2 arms combined along with 95% CI. Analyses will be performed for ITT and MITT populations.

4.2. Secondary and Exploratory Efficacy Endpoints

4.2.1.1. Overall Response and MRD Negativity

Number and percent of participants achieving the following best response outcomes, along with 95% CI, will be provided:

- CRh
- CRi
- MLFS
- CR+CRh
- CR+CRh+CRi (overall response rate, ORR)
- PR
- SD
- PD
- CR without MRD

Subgroup analysis will be provided for ORR as forest plots.

4.2.1.2. Time to Response

Time to response is defined as the time from randomization to achieving the first response of CR, CRh, or CRi for participants who achieved such a response. Descriptive statistics will be summarized by treatment arm using the Kaplan-Meier method (with no censored observations).

4.2.1.3. Duration of Response

Duration of response is defined for participants who achieved the first response of CR, CRh, or CRi as the time from achieving such a response to relapse or deaths due to any cause. Duration will be censored at the time of last tumor assessment for participants who did not relapse or die. Duration of response will be summarized descriptively using the Kaplan-Meier method.

4.2.1.4. Transfusion Independent

Number and percent of participants achieving transfusion independence (TI), along with 95% CI, will be provided for:

- Red blood cell TI
- Platelets TI
- Red blood cell and platelets TI

Time to and duration of transfusion independence for participants achieving TI will be summarized similarly to time to and duration of response. Time to TI is calculated from randomization to 1 day after the last transfusion episode prior to achieving TI; and duration of TI is calculated from the day of achieving TI to the day of the first transfusion episode after the TI period.

Summaries will be provided for red blood cell and platelet transfusions separately. The number and percent of participants who received transfusions from the date of randomization to 30 days after the last dose will be summarized by treatment arm.

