3. OBJECTIVES AND ENDPOINTS

Objectives	Endpoints
Primary	
To determine the efficacy of cusatuzumab in combination with azacitidine in patients with previously untreated AML who are not eligible for intensive chemotherapy	Complete response (CR) rate per ELN 2017 (Dohner 2017) ⁶
Secondary	

To determine other response measures (see definitions in Table 6)
 
To assess time to response and duration of response
 
To determine transfusion independence
 
To assess the safety profile of cusatuzumab in combination with azacitidine
 
To assess the pharmacokinetics of cusatuzumab alone and in combination with azacitidine
	
 • Rate of CRh • Rate of CR + CRh • Rate of CRi • Overall response rate (ORR) = Rate of CR+ CRh+ CRi • Rate of CR without MRD • Rate of MRD negativity among participants achieving CR, CRh, CRi, or MLFS; defined as less than 1 blast or leukemic stem cell in 1,000 leukocytes (MRD level $<10^{-3}$) 
Time to response, defined as time from randomization in Part 1 or enrollment in Part 2 to achieving the first response of CR, CRh, or CRi; duration of response, defined as time from achieving the first response of CR, CRh, or CRi to disease relapse or death from any cause.
 
Transfusion independence (RBC or platelets) is defined as a period of at least 56 consecutive days with no transfusion between first dose of study drug and the last dose of study drug + 30 days.
 
Safety profile of Adverse Events (AE) and Serious Adverse Events (SAE)
 
Pharmacokinetics

Objectives	Endpoints
To assess the immunogenicity of cusatuzumab alone and in combination with azacitidine	Immunogenicity / anti-drug antibody testing
Exploratory	
To assess progression-free survival (PFS)	PFS is defined as the time from randomization in Part 1 or enrollment in Part 2 to progressive disease, relapse from CR/CRh/CRi, or death from any cause, whichever occurs first.
To assess overall survival (OS)	OS is defined as the time from randomization in Part 1 or enrollment in Part 2 to death
To assess pharmacodynamics and to explore biomarkers predictive of clinical response	Exploratory biomarkers including baseline level of CD70+ blasts, CD70+LSC, sCD27, NK cells
To assess patient-reported symptom severity and health-related quality of life	PROs using the FACT-Leu and EQ 5D 5L (See Section 10.8 Appendix 8 and Section 10.9 Appendix 9)

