1.1.2. Secondary and Exploratory Objectives

Secondary objectives are to evaluate the following:

- Rate of CRh
- Rate of CR + CRh
- Rate of CRi
- Overall response rate (ORR) = CR + CRh + CRi
- Rate of CR without MRD
- Time to response, defined as time from randomization/enrollment to achieving the first response of CRi, CRh, or CR
- Duration of response, defined as time from achieving first response of CRi, CRh, or CR to disease relapse, progression or death of any cause
- Safety profile of adverse events (AE) and serious adverse events (SAE)
- Transfusion independence (TI), defined as having a period of at least 56 consecutive days with no red blood cell or platelets transfusion between randomization and the last dose of study drug + 30 days
- Pharmacokinetics (PK) of cusatuzumab alone and in combination with azacitidine
- Immunogenicity/anti-drug antibody of cusatuzumab alone and in combination with azacitidine

Exploratory objectives are to summarize the following:

- Progression-free survival (PFS), defined as the time from randomization (part 1) or enrollment (part 2) to progressive disease, relapse from CR/CRh/CRi, or death from any cause, whichever occurs first
- Overall survival (OS), defined as the time from randomization (part 1) or enrollment (part 2) to death from any cause

- Exploratory biomarkers including baseline level of CD70+ blasts, CD70+ LSC, sCD27, NK cells: to assess the pharmacodynamics and to explore biomarkers predictive of clinical response
- PROs using the FACT-Leu and EQ 5D 5L

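### The transfusion independence (TI) rate cannot be read as conversion, and time to TI has no valid value for some participants who achieve it

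*SAP*

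**What the plan says.** - **Definition.** Protocol 3 defines TI as "a period of at least 56 consecutive days with no transfusion between first dose of study drug and the last dose of study drug", plus 30 days. SAP 1.1.2 asks for "at least 56 consecutive days with no red blood cell or platelets transfusion between randomization and the last dose of study drug", again plus 30 days. The window opens at first dose in one document and at randomization in the other. Neither mentions transfusion need before treatment.
- **Rate.** SAP 4.2.1.4 plans "Number and percent of participants achieving transfusion independence (TI), along with 95% CI", for red cells, platelets and both. On the denominator, SAP 2.1 says "ITT will be used for all summaries of disposition, demographic, baseline disease characteristics, and efficacy analyses".
- **Timing.** SAP 4.2.1.4: "Time to TI is calculated from randomization to 1 day after the last transfusion episode prior to achieving TI". It adds: "Time to and duration of transfusion independence for participants achieving TI will be summarized similarly to time to and duration of response". SAP 4.2.1.2 summarizes time to response by Kaplan-Meier with every observation uncensored.
- **Related summaries.** SAP 4.2.1.4 also reports, by arm, the share of participants transfused on study. SAP 2.2 plans subgroups for overall response rate only, and baseline transfusion status is not among them.

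**The concern.** A participant who needed no transfusions at entry, and needs none for 56 days on study, counts as achieving TI. Such participants are foreseeable. The eligibility criteria set no transfusion or platelet requirement, SAP 2.2 plans a subgroup with platelets at or above 100, and Protocol 6.6.3 has azacitidine text for patients whose baseline counts are not reduced. The TI percentage therefore depends on who was enrolled as well as on what happened under treatment, and nothing planned separates the two.

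Both arms receive cusatuzumab plus azacitidine, so each arm's TI percentage and interval will largely be read on its own. A reader may take it as the share freed from transfusion, which it is not.

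The timing rule needs a transfusion date that some achievers do not have. Because time to TI is to be summarized like time to response, with no censoring, every achiever is implied to have a time. Whoever programs the table must then decide, with data in view, whether to drop, floor or keep these cases.

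**Working it through.** The documents state no expected rate, event count or power for TI, so there is no figure to reproduce. The check applies the SAP's own rules.

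**Step 1: the rate.** Let q be the share independent at baseline, a the share of those with 56 free days on study, and c the conversion rate among the rest. Over all ITT participants:

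TI rate = q·a + (1 − q)·c

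None of the three inputs is in the documents. Assumed ranges: q 20% to 60%, a 60% to 80%, c 0% to 40%.

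| c | Lowest (q = 20%, a = 60%) | Highest (q = 60%, a = 80%) |
|---|---|---|
| 0% | 0.20 × 0.60 = 12% | 0.60 × 0.80 = 48% |
| 20% | 0.12 + 0.80 × 0.20 = 28% | 0.48 + 0.40 × 0.20 = 56% |
| 40% | 0.12 + 0.80 × 0.40 = 44% | 0.48 + 0.40 × 0.40 = 64% |

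With 50 participants in an arm, 12% to 48% is 6 to 24 participants counted as achieving TI although nobody converted.

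For a contrast between doses with equal q and a, the difference in TI rate is (1 − q) times the difference in c. A true 20-point difference in conversion appears as 0.80 × 20 = 16, 0.60 × 20 = 12 or 0.40 × 20 = 8 points at q = 20%, 40% or 60%.

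**Step 2: the time.** Let d be the date of the last transfusion before TI minus the randomization date. The end point is d + 1, and SAP 2.3 counts days as end minus start plus one, so time to TI = (d + 1) + 1 = d + 2 days.

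| Last transfusion before TI | Time to TI (days) |
|---|---|
| 30 days after randomization | 32 |
| Day of randomization | 2 |
| 1 day before | 1, if pre-randomization transfusions count |
| 2 days before | 0, on the same condition |
| 3 days before | −1, on the same condition |
| 7 days before | −5, on the same condition |
| 28 days before | −26, on the same condition |
| Never transfused | no value |

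The SAP does not say whether pre-randomization transfusions count. If they do not, all the rows for earlier transfusions also have no value. If they do, the dates may exist: Protocol 6.5 has prior therapies recorded for 28 days before first dose, and Table 1 lists transfusion status at screening.

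**Step 3: the window.** Table 1 puts randomization within 72 hours of first dose, so the two window starts differ by about 3 days at most. A window from first dose to 30 days after the last dose reaches 56 days only if the last dose falls on Day 26 or later (26 + 30 = 56). A never-transfused participant whose last dose is Cycle 1 Day 17 has 17 + 30 = 47 days and does not count. The rate therefore captures baseline-independent participants only if they stay on treatment long enough, which is one reason to take a below 100%.

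**The case against.** The strongest reply is that the TI rate is coherent as written. The objective is to determine transfusion independence, neither document calls the result a conversion rate, and the share of all randomized participants with 56 free days is a legitimate ITT summary. That stands, and the rate should be kept. It does not supply the conversion figure that a reader will look for, and the on-study transfusion percentage does not show baseline status.

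A reader might infer that neither TI result carries information about treatment. The documents do not support that. The rate contains conversions and moves with them. Randomization balances baseline need between the doses in expectation, so a dose contrast is diluted but not removed. Times are valid for everyone transfused between randomization and TI.

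A reader might also infer that participants who never needed transfusion get negative times. They get none. Zero or negative values need a pre-randomization transfusion two or more days earlier, and a reading of the SAP that counts it. Since the TI window and the companion transfusion count both open at randomization, counting only on-study episodes is arguably the more natural reading. On that reading the problem is missing values, not negative ones.

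Finally, SAP 1.6 makes Part 1 descriptive with no formal comparison, and Part 2 was dropped. That lowers the stakes but does not define an undefined date.

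**Conclusion.** The point holds in two parts. First, the TI rate mixes maintained with converted independence and cannot be read as conversion. Under the assumed ranges it could be 12% to 48% with no conversion. Those figures show how far baseline need can drive the result; they do not predict this trial. Second, time to TI is incompletely specified. It has no value for achievers without a transfusion between randomization and TI or, if earlier transfusions count, can be zero or negative for some of them. This part follows from the text and needs no assumed rate. The difference in window start is a small wording mismatch. Because TI is secondary and descriptive, severity is modest, but the split by baseline need is a better analysis and not merely added detail.

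**What to change.** In SAP 4.2.1.4:

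1. Keep the all-ITT TI rate.
2. Define baseline transfusion need with a stated look-back that ends where the TI window opens, for example using the 28 days before first dose already recorded under Protocol 6.5. Confirm that transfusion dates are held for that period.
3. For red cells, platelets and both, report conversion (TI among those transfused in the look-back) and maintenance (TI among those not).
4. Summarize time to TI for achievers with a transfusion in the look-back or on study before TI. When the last transfusion precedes the window, set the time to the window start (Day 1). Exclude never-transfused achievers and report their number. Limiting time to TI to those transfused at baseline would wrongly drop participants first transfused on study, for whom the present formula works.
5. Use one window start in both documents.

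The cost is SAP wording and less precision for conversion. With 50 per arm and q of 20%, 40% or 60%, the conversion denominator is 50 × (1 − q) = 40, 30 or 20. At the same percentage the interval widens by roughly √(50/40) = 1.1, √(50/30) = 1.3 or √(50/20) = 1.6 times. One limit remains: a participant last transfused during screening counts as converted although that transfusion came before any study drug, so the conversion rate describes the arm and does not isolate a drug effect.
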